11.3 SAE Reporting Procedures

Serious adverse events that occur starting from the signing of the informed consent form until 28 days (inclusive) after the last dose should be reported. Any SAE occurring during the trial must be immediately reported to the clinical research associate (CRA), the principal investigator, the PLA Tumor Center of the 81st Hospital of the Chinese People's Liberation Army and the Medical Director of Jiangsu Hengrui Pharmaceuticals Co., Ltd. via fax or phone. Meanwhile, the "New Drug Clinical Trial Serious Adverse Event (SAE) Report Form" should be completed, signed, dated, and submitted to NMPA within 24 hours.

During the continued treatment period, SAE should be reported to the sponsor within 24 hours. All information regarding the SAE should be documented in the SAE form. SAEs that occur during the continued treatment period until 28 days after the last dose should also be reported. SAEs that occur 28 days after the last dose are generally not reported unless suspected to be related to the investigational drug.

SAEs should be documented in detail, including symptoms, severity, date of onset, time of treatment, measures taken, time and method of follow-up, as well as outcome. If the investigator believes that an SAE is unrelated to the investigational drug but potentially related to study conditions (e.g., termination of the original treatment, or complications during the trial), then this relationship should be detailed in the SAE page of the case report form. If the severity of an ongoing SAE or its relationship to the investigational drug changes, a follow-up report of the SAE should be submitted to Jiangsu Hengrui Pharmaceuticals Co., Ltd. immediately. All SAEs should be followed until resolved or stabilized.

Table 13. Contact information of each institution

Institution	Contact	Telephone	Fax
National Medical Products Administration	Safety Supervision Department	[name]	[name]
PLA Tumor Center of the 81 st Hospital of the Chinese People's Liberation Army	[name] [name]	[name]	[name]
Jiangsu Hengrui Pharmaceuticals Co., Ltd.	[name]	[name]	[name]

11.4 Emergency Unblinding

The emergency unblinding table is a sealed document provided by the sponsor that contains the treatment allocation for each subject. Unless there is a mandatory medical reason, the investigator should not unblind the subjects at will. Only when a subject experiences an emergency situation such as an SAE, the responsible investigator at the study site and the principal investigator can jointly decide whether to unblind. The blind code should be kept by dedicated technicians from the Department of Epidemiology and Health Statistics of Nanjing Medical University. If unblinding is necessary, the medical director of the sponsor should be notified and the dedicated technicians should be contacted to obtain the blind code within 24 h. Once unblinded, the subject should immediately withdraw from the trial.

11.5 Safety Monitoring Committee

During the trial, a drug safety monitoring committee composed of the principal investigator, the medical director of Hengrui and the person in charge of drug safety will be established to review the safety data generated during the trial. If a significant safety signal is found, such as the occurrence of an SAE or the need to interrupt the treatment, the drug safety monitoring committee can also host meetings to review and discuss the corresponding relationship between the safety data and the drug along with major changes to the protocol.

12 DATA MANAGEMENT AND STATISTICAL ANALYSIS

12.1 Data Collection and Management

Data will be collected and managed using the electronic case report form (eCRF).

12.1.1 Data collection

Data will be collected using the eCRF. Jiangsu Hengrui Pharmaceuticals Co., Ltd. will provide an electronic data capture (EDC) system. Company staff will deliver EDC system training to the designated staff of study site. Access to EDC system will only be granted to the study site staff who have completed the training. The PI or dedicated data entry person (CRC) should input data into the EDC system in accordance with the requirements of the visit procedures and the eCRF completion guide. The logic verification program in the system will verify the integrity and logic of the clinical trial data entered into the EDC system

and generate an error message prompt for questionable data. The PI or CRC is permitted to modify or explain the problematic data. After the database is locked, the investigator will receive a CD-ROM or copy of subject data to archive at the study site.

12.1.2 Data management and quality control

To ensure authenticity and reliability and improve the quality of the clinical data, the CRA will monitor the integrity, consistency, and accuracy of the trial data in the database, and guide the study site staff to add or correct the data whenever necessary. The CRA or data manager will send electronic query form to the PI or CRC for problematic data. The PI or CRC must respond and provide correction or explanation of the problematic data. Multiple queries may be raised when necessary until the problem is solved. The medical director and data manager should perform consistency comparison of SAEs periodically.

At the end of the study, the data manager and medical personnel will conduct a final quality control on all data in the database, summarize all protocol deviations and violations during the trial, and hold a data verification meeting. Database locking and unblinding will be carried out after the quality requirements have been met. The data manager will export the data to the statistics department for data analysis.

12.1.3 Data review and study site monitoring

Before the initiation of the study, a representative from Jiangsu Hengrui Pharmaceuticals Co., Ltd. will introduce study protocol and eCRF (Part 2) to the investigator and staff at the initial visit to the study site. During the study, the CRA will visit the study site regularly to monitor the completeness of the subject's records and the accuracy of the eCRF, compliance with the study protocol and GCP, and enrollment progress, and to ensure that the investigational drugs are stored, dispensed, and counted as required. During these visits, the major research personnel are required to assist the work of CRA.

The investigator must keep the source documents of each subject, including all medical records and visit records (outpatient or inpatient record), such as demographic indicators, medical information, lab results, ECGs, and result of other examinations and evaluations. All information on the eCRF must come from the source documents of the subject. The investigator must also keep the informed consent forms signed by the subjects.

The investigator must ensure all source documents are available for monitoring to verify the consistency with the eCRF. Jiangsu Hengrui Pharmaceuticals Co., Ltd. requires to completely monitor the signed informed consent forms, compliance with inclusion/exclusion criteria, SAEs records, and all data required for evaluation of primary endpoints and safety endpoints. Additional monitoring will be performed on consistency of source data and eCRF according to monitoring plan specified by the trial. No information related to subjects' identity in the source document will be disclosed.

12.2 Statistical Analysis of Trial Data

- Full analysis set (FAS): According to the intention-to-treat (ITT) principle, all randomized subjects who have received 1 dose of study medication are included for efficacy analysis. For subjects whose entire course of treatment cannot be observed, the last observation data can be transferred to the final study results (LOCF).
- Per-protocol set (PPS): All subjects who are in compliance with the protocol, have good compliance, have received at least 1 cycle of treatment (except for those with clear medical evidence of PD), and have completed the eCRF according to protocol requirements, and have not taken any prohibited medications during the trial. No imputation is made for missing data. The statistical analysis will be performed for the drug efficacy based on the FAS and PPS. Before database locking, the principal investigator, statistician, and sponsor should determine the final PPS during the data review meeting.
- Safety analysis set (SAS): All enrolled subjects who have received at least one dose of the investigational drug and have safety data after the dose are included in the safety set. This dataset is used for safety analysis.

12.3 Statistical Analysis Plan

Time for efficacy analysis and safety assessment: Based on the full analysis set, when 312 deaths ($\geq 80\%$ of patients died) occur, a final verification of the data in eCRF shall be performed. After the data integrity is verified and all quality assurance (QA) and quality control (QC) procedures on the data management are performed, the randomization protocol must be disclosed, and the data from the clinical database will be retrieved to record and statistically analyze the efficacy and safety data. In the efficacy analysis, the data cutoff date is the date when the 312th death occurs. In the analysis of overall survival (OS), if the subject does not die at or before the cutoff date, and if there are data (study visits, survival follow-ups, etc.) confirming that the subject has died or is still alive after the cutoff date, the subject data will be reviewed on the cutoff date. If the last date of known survival of a subject is before or at the cutoff date, the data of the subject will be reviewed on the day of last known survival. In the analyses of progression-free survival (PFS) and time to disease progression (TTP), if the subject has neither disease progression events (for TTP and PFS) nor death (for PFS only) at or before the cutoff date, then the data of the subject will be reviewed on the subject's last day of radiographic tumor assessment on or before the cutoff date, except for the following case: For any radiographic tumor assessment as per the RECIST v1.1 criteria that indicates no evidence of progression, the review date will be set as the cutoff date.

Pre-set subgroup analysis: Subgroups will be pre-defined based on the following factors for a confirmatory subgroup analysis in this study: age \leq 65 years or $>$ 65 years; ECOG score 0 or 1; with or without vascular invasion; with or without extrahepatic metastases; with or without vascular invasion and extrahepatic metastases; positive or negative HBV; and with or without past history of sorafenib treatment.

All statistical analyses will be performed using SAS. All statistical analyses are performed using two-tailed tests. $P \leq 0.05$ is considered statistically significant, and 95% confidence is used for confidence intervals.

Analyses were performed as per groups based on the initial dose and the dose at the end of treatment, respectively.

The baseline data is analyzed based on the full analysis set (FAS). All efficacy endpoints are analyzed based on the FAS and the per protocol set (PPS). The analysis of primary efficacy endpoint OS is carried out mainly in the ITT, but the PPS is additionally used for verification in the final analysis. The safety analysis is carried out based on the safety analysis set (SS).

The measurement data obtained from various treatment groups during various visits will be statistically described by mean \pm standard deviation or median (minimum, maximum). For comparison with baseline values of the screening period, paired t-tests are used to compare pre and post intra-group differences. Changes occurring in each group before and after treatment should be compared by the analysis of variance (ANOVA) or rank sum test. The frequency data obtained from various treatment groups during various visits will be statistically described by frequency (proportions). Changes occurring in each group before and after treatment should be compared by χ^2 test (exact test) or nonparametric test.

- **Dropout analysis:** Descriptive analysis is mainly used. If necessary, the total dropout rate of each group and the comparison of dropout due to AEs will be tested by χ^2 test or Fisher's exact test.
- **Balance analysis of baseline values:** ANOVA or χ^2 test is used to compare demographic data and other baseline values to evaluate the balance of various groups.

The demographics include: age, gender, course of disease, ECOG PS, pathological grade, clinical stage, vascular invasion and/or extrahepatic metastasis (such as portal vein invasion, N1 (regional lymph node metastasis) or M1 (distant metastasis), yes or not), past treatment (surgical history of primary lesions, history of interventional procedures, history of radiotherapy, history of neoadjuvant chemotherapy), etiology of liver cancer (HBV infection, HCV infection, alcoholic cirrhosis or other), and α -fetoprotein (AFP) (low, normal, or high).

All statistical parameters and analyses at baseline are determined based on characteristics obtained before first study medication (before randomization for subjects who have not received treatment). Unless otherwise stated, the baseline value of a specific variable is defined as the last value of the parameter obtained before the first study medication.

- Efficacy analysis:

For the comparison of 3-, 6-, and 12-month PFS rates, objective response rate (ORR), disease control rate (DCR), the percentage of patients with stable disease (SD) of ≥ 4 weeks (confirmed SD in particular), and 6- and 12-month mortalities, CMH- χ^2 tests with and without central stratification are used to compare the efficacy between the two groups. In addition, the 95% confidence interval of the difference between the two groups is also calculated. Based on the product limit method and the actual condition of the data, 25%, 50% (median) and 75% of PFS and TTP, as well as PFS and OS at different time points after the start of treatment, are calculated and the endpoints are compared between the two groups using the Log-Rank test.

- Safety analysis: Descriptive statistical analysis will be mainly used. The AEs and SAEs, treatment-related AEs and SAEs, and AEs and SAEs of special interest (e.g., hypertension, proteinuria, and hand-and-foot syndrome) are listed and summarized. If necessary, the incidence and severity of AEs and SAEs between different groups are compared using Fisher's exact test. For laboratory results, the cases in which the pre-treatment values are normal but the post-treatment values are abnormal will be described, and the relationship between the abnormal changes and the investigational drug will be evaluated.

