Placebo group: Placebo is given via oral administration after meals (the dosing time on each day should remain the same whenever possible) at an initial dose of 750 mg/day, once a day, 3 tablets per dose, in 28-day cycles. The dose can be adjusted based on the toxic reactions of the subjects as per protocol (first dose reduction: 500 mg/day, q.d.; second dose reduction: 250 mg/day, q.d.);

Study Period

November 2013-March 2018

In this trial, placebo is used as a control and a superiority test is performed between the two groups.

All statistical analyses will be performed using SAS. All statistical analyses are performed using two-tailed tests. $P \leq 0.05$ is considered statistically significant, and 95% confidence is used for confidence intervals.

Pre-set subgroup analysis: Subgroups will be pre-defined based on the following factors for a confirmatory subgroup analysis in this study: age ≤ 65 years or > 65 years; ECOG PS 0 or 1; with or without vascular invasion; with or without extrahepatic metastases; with or without vascular invasion and extrahepatic metastases; positive or negative HBV; and with or without past history of sorafenib treatment.

The baseline data is analyzed based on the full analysis set (FAS). All efficacy endpoints are analyzed based on the FAS and the per protocol set (PPS). The analysis of primary efficacy endpoint OS is carried out mainly in the FAS, but the PPS is used for the final analysis. The safety analysis is carried out based on the safety analysis set (SS).

The measurement data obtained from various treatment groups during various visits will be statistically described by mean \pm standard deviation or median (minimum, maximum). For comparison with baseline values of the screening period, paired t-tests are used to compare pre and post intra-group differences. Changes occurring in each group before and after treatment should be

Statistical Methods

compared by the analysis of variance (ANOVA) or rank sum test. The frequency data obtained from various treatment groups during various visits will be statistically described by frequency (proportions). Changes occurring in each group before and after treatment should be compared by χ^2 test (exact test) or nonparametric test.

- Dropout analysis: Descriptive analysis is mainly used. If necessary, the total dropout rate of each group and the comparison of dropout due to AEs will be tested by χ^2 test or Fisher's exact test.

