#### **7.1.1 Significance level**

For group comparisons, all hypothesis tests are performed using two-sided tests with an  $\alpha = 0.05$ . If  $P$  is  $\leq 0.05$ , the difference of the test is considered to be statistically significant. A 95% confidence interval is used in this study.

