## 7.6 Other Analyses

### 7.6.1 Subgroup analysis

Subgroup analyses are performed for the primary efficacy endpoint according to the following factors, and the forest plot on HR is produced:

Age ( $\leq 65$  years old,  $> 65$  years old)

ECOG PS (0, 1)

Presence of vascular invasion (yes, no)

Presence of extrahepatic metastasis (yes, no)

Presence of vascular invasion and/or extrahepatic metastasis (yes, no)

Treatment with sorafenib (yes, no)

Previous systemic treatment line(s) (one line,  $\geq$  two lines)

HBV (positive, negative)

Alpha-fetoprotein (AFP  $< 400\mu\text{g/L}$ ,  $\geq 400\mu\text{g/L}$ )

Alpha-fetoprotein (AFP  $< 200 \mu\text{g/L}$ ,  $\geq 200 \mu\text{g/L}$ )

Child-Pugh score (Grade A, Grade B)

BCLC stage (B, C)

Previous liver transplant (yes, no)

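### The protocol calls a seven-factor subgroup analysis confirmatory with no test, decision rule or error control, and the SAP does not withdraw the label

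*Protocol*

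**What the plan says.** **Protocol.** Section 12.3 introduces the subgroup list with "Subgroups will be pre-defined based on the following factors for a confirmatory subgroup analysis in this study". The Statistical Methods part of the synopsis also has "for a confirmatory subgroup analysis in this study". The factors are age (cut at 65), ECOG score, vascular invasion and extrahepatic metastases, followed by "with or without vascular invasion and extrahepatic metastases; positive or negative HBV; and with or without past history of sorafenib treatment". That makes seven two-level factors, and the fifth is built from the third and fourth. The next paragraph of 12.3 sets a general rule: "All statistical analyses are performed using two-tailed tests", with P at or below 0.05 counted as significant. For the subgroups the protocol gives no endpoint, no test (within-subgroup or interaction), no success rule, no testing order and no alpha split.

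**SAP.** Section 7.6.1, under Other Analyses, reads: "Subgroup analyses are performed for the primary efficacy endpoint according to the following factors, and the forest plot on HR is produced". It lists 13 factors. It names no subgroup test and does not use the word confirmatory, but it does not call the subgroups exploratory either. Section 7.1.1 repeats the general rule for group comparisons: "all hypothesis tests are performed using two-sided tests" at 0.05. Section 7.4.1, by contrast, says expressly that P values comparing adverse event incidences are for clinical reference and not for statistical inference.

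**Where the efficacy conclusion rests.** Protocol 4.2 bases superiority on the overall OS comparison: a significant hazard ratio that is also no greater than 0.84. SAP 7.1.2 states one hypothesis pair, apatinib against placebo. SAP 7.3.1 names one primary test, the stratified log-rank test of OS in the full analysis set.

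**The concern.** A confirmatory analysis needs a stated hypothesis, a test, a decision rule and control of the error rate across the family. The protocol gives the subgroup analysis the name and none of these. The SAP describes a different and more modest analysis but leaves the name standing, so the two documents together do not settle what status a subgroup result has.

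This matters in both directions:

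- If overall OS misses significance, a favourable subgroup could be described as prespecified and confirmatory, with the protocol as the reference.
- If overall OS succeeds, a subgroup with a non-significant result could be read as confirmed absence of benefit, when low power would be a likely explanation.

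The factor lists also differ (7 against 13), and so does the combined factor. The protocol's subgroup list joins vascular invasion and extrahepatic metastases with *and*; SAP 7.6.1 uses *and/or*, as does the stratification factor in Protocol 4.4. A family that is not defined the same way in both documents cannot carry a confirmatory claim.

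**Working it through.** **Inputs from the documents.** Median OS 8.5 against 6 months, two-sided 0.05, 80% power, 2:1 allocation, 15% loss to follow-up, 12 months' accrual, 36 months in total (Protocol 4.3, SAP 2.4); 390 subjects and analysis at 312 deaths (Protocol 4.3 and 12.3); seven two-level factors (Protocol 12.3).

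**Step 1: the plan's own figure.** The documents state no subgroup error rate; the nearest design figure is the total of 331.
- HR = 6/8.5 = 0.706 under exponential survival.
- Schoenfeld: (1.960 + 0.842)² / [(2/3)(1/3)(ln 0.706)²] gives 292 deaths.
- With uniform accrual and constant loss reaching 15% by month 36 (an assumption; the software settings are not given), the death probabilities are 0.934 on placebo and 0.873 on apatinib. The pooled value is (0.934 + 2 × 0.873)/3 = 0.893.
- 292/0.893 ≈ 327, close to 331. The trial was sized for one overall OS comparison.

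**Step 2: one test per factor.** If the seven tests were independent, 1 − 0.95⁷ = 0.302.

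**Step 3: simulation, keeping the reuse of patients.** 390 subjects, 2:1, 312 deaths, no treatment effect, log-rank statistics, 4,000 runs per scenario. The documents give no subgroup prevalences, so three sets were assumed, with minority levels from 10% to 50%. Factors were drawn independently, except the combined one, which was built from its two components either as a union (*and/or*) or as an intersection (*and*). Ranges over the six scenarios:

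| Event, with no true effect | Chance |
|---|---|
| At least one of 14 level-specific tests at two-sided 0.05 | 0.33–0.37 |
| Same, counting only results favouring apatinib | 0.19–0.21 |
| At least one of seven interaction tests at 0.05 | 0.29–0.31 |
| Overall OS significant for apatinib and at least one level significant | about 0.03 |

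The last row is what a gate on overall OS would leave. No such gate is written. Subtracting overall OS significance in favour of apatinib (0.025–0.032) from the second row, scenario by scenario, leaves about 0.16–0.18: a favourable subgroup although overall OS has not shown benefit.

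**Step 4: an adjusted family, for comparison.** Bonferroni over seven tests gives 0.05/7 = 0.0071 each, and 1 − (1 − 0.0071)⁷ ≈ 0.049.

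**Step 5: power within a subgroup.** For a level holding half the deaths (156) at HR 0.706: √(156 × 2/9) × 0.348 − 1.960 = 0.09, so power is about 54%. The same formula with all 312 deaths gives 83%.

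**The case against.** The strongest reply is that nothing in the plan turns a subgroup result into an efficacy conclusion. Protocol 4.2, SAP 7.1.2 and SAP 7.3.1 all tie that conclusion to the overall OS comparison. SAP 7.6.1 is the more detailed specification and plans hazard ratios in a forest plot, with no P value. On this view the 0.05 is a general rule with no subgroup test to attach to. The protocol is also a translation: in 12.3 subjects' data are said to be reviewed on dates where censoring is evidently meant, so *confirmatory* may be loose wording too.

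Most of this stands, and it limits the point. Three stronger readings are tempting and should not be drawn:

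- *The plan as written carries a one-in-three chance of a false subgroup claim.* No subgroup test is specified, so the percentage describes what would follow if the protocol wording were acted on, not the forest plot in the SAP. The two-sided figure also counts results favouring placebo; a false claim of benefit corresponds to about one in five.
- *The chance is 51%, from 1 − 0.95¹⁴.* That treats 14 tests as independent, but the seven factors divide the same patients and one factor is built from two others.
- *The trial's overall type I error is inflated.* The single primary test is untouched.

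What the reply does not do is remove the label. The word appears in two operative places in the protocol, and the SAP does not withdraw it, although SAP 7.4.1 shows that its authors mark non-inferential P values when they intend to. Whether the translation is at fault cannot be established from these documents, and the correction would be the same.

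**Conclusion.** The point holds as an unsupported status and an inconsistency between documents. It is not an error in the primary analysis. The protocol gives seven overlapping factors confirmatory standing with none of the apparatus that would justify it, and the SAP plans a descriptive display without saying so.

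The error figures in the table are conditional on three things: testing every level (or every interaction) at 0.05, no effect anywhere, and the assumed prevalences. Across the scenarios the prevalences changed the results little. The main uncertainty is which test the protocol intended, since the documents do not say. Because relabelling changes what may legitimately be concluded from a subgroup and costs almost nothing, it should be done.

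**What to change.** 1. In the synopsis and Protocol 12.3, replace *confirmatory* with *exploratory*.
2. In SAP 7.6.1, state that subgroup hazard ratios and 95% confidence intervals are descriptive and cannot support an efficacy claim, whatever the overall OS result.
3. Report a treatment-by-subgroup interaction test for each factor as supportive only. State the number of tests, and base no claim on an unadjusted P at or below 0.05. The restriction is needed because seven such tests themselves carry about a 30% chance of a false positive; 13, if independent, would carry 1 − 0.95¹³ = 0.49.
4. Align the lists: 7 or 13 factors, and *and* or *and/or* for vascular invasion and extrahepatic metastasis.

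The cost is a few sentences and one interaction term per factor. Design, sample size and primary analysis do not change. The downside is that the sponsor gives up a confirmatory subgroup claim, which the design could not have supported.
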